Twenty four-hour urine will be collected at each ambulatory visit (Visit 2, Visit 3, and Visit 4) at the site. The collection of 24-hour urine will start on the first day of the respective visits and will end 24 hours later on the following day. On the first day of Visit 2, Visit 3, and Visit 4, subjects in the CHTP 1.2 and CC arms will be allowed to use their assigned product from the time of check-in until 11:00 PM. On the second day of Visit 2 and Visit 3 product use will be allowed from 06:30 AM onwards. The exposure period to the assigned IP will end at 11:00 PM on the first day of Visit 4.

On the second day of Visit 4 (Day 91), subjects who wish to smoke CC or use other nicotine/tobacco-containing products will be allowed to do so, but only after the end of 24-hour urine collection and after spirometry and sampling for CYP2A6 activity have been performed.

During the visits, the dispense and use of CHTP 1.2 will be strictly forbidden for subjects in the CC arm.

Subject will not be discontinued from the study for the use of nicotine/tobacco containing products other than the assigned product/regimen during the ambulatory period. Subjects will record in a product use diary any use of CC (menthol or non-menthol), Nicotine replacement therapy (NRT), or other nicotine/tobacco-containing products on a daily basis.

During the confinement and ambulatory settings:

- Any subject, who wants to attempt to quit using any tobacco products during the study taking into account the outcome from the Prochaska “Stages of Change” Questionnaire, will be encouraged to do so and will be referred to appropriate medical services. This will not affect subject’s financial compensation and the subject will remain in the study.
- The Safety Follow-up Period (from Discharge at Visit 4 until the end of the Safety Follow-up Period):

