09:00 AM ± 30 min		Start of 24-hour urine sample collection for Day 30 (the first day of Visit 2) / Day 60 (the first day of Visit 3)	The subject must empty his/her bladder and discard the urine prior to starting urine collection. The urine is collected for 24 hours ±1 hour
During the visit		CO breath test	Irrespective of the time of product use
During the visit	√	COHb in blood	Irrespective of the time of product use
During the visit	√	Plasma nicotine and cotinine sample	Cotinine will be measured in the same assay as nicotine. No additional blood samples required
During the visit		Vital signs (blood pressure, pulse rate, respiratory rate)	At least 5 minutes in supine position, at least 15 minutes after having stopped using IP
During the visit		Physical examination, body weight, and calculated BMI	
During the visit		Urine pregnancy test (females only)	
8:00 PM - 11:00 PM		QSU brief Questionnaire	
8:00 PM - 11:00 PM		MCEQ Questionnaire	
11:00 PM		End of use of IPs	
During the visit		Product use diary	To be completed by the subject. All IPs used including CHTPs 1.2, CC, and any tobacco/nicotine containing products have to be recorded
During the visit		Collection of empty/partially used CHTP 1.2 packs for accountability	At any time of the day Partially used packs will be returned to the subject

Confidentiality Statement

Data and information contained in this document are considered to constitute trade secrets and confidential commercial information, and the legal protections provided to such trade secrets and confidential information are hereby claimed under the provisions of applicable law. No part of this document may be publicly disclosed without the written consent of Philip Morris Products S.A.

Time	Blood Sample	Procedures	Additional Information
Start of Procedure		Day 30 / Day 60	

Abbreviations: AE = Adverse event; BMI = Body mass index; CC = Combustible cigarette(s); CHTP 1.2 = Carbon Heated Tobacco Product 1.2; CO = Carbon monoxide; COHb = Carboxyhemoglobin; IP = Investigational product; MCEQ = Modified Cigarette Evaluation Questionnaire; QSU-brief = Questionnaire of Smoking Urges (brief version); SAE = Serious adverse event

Table 16 shows the assessments that will be performed on the second day of Visit 2 and of Visit 3 of the ambulatory period.

Table 16 Time Schedule – The Second Day of Visit 2 (Day 31), The Second Day of Visit 3 (Day 61)

Time	Blood Sample	Procedures	Additional Information
Start of Procedure		Day 31 / Day 61	

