During the visit		AE/SAE recording	
During the visit		Concomitant medications	
		End of 24-hour urine sample collection for Day 30 (the first day of Visit 2) / Day 60 (the first day of Visit 3)	The urine is collected for 24 hours \pm 1 hour
		Urine sample to be taken from the 24-hour urine of Day 30 (the first day of Visit 2) / Day 60 (the first day of Visit 3)	Aliquots from 24-hour urine will be collected according to Table A2 .
Prior to 11:30 AM	√	Clinical laboratory parameters* (hematology, clinical chemistry) and cardiovascular clinical risk endpoints (hs-CRP, MPO, fibrinogen, homocysteine, LDL, HDL, sICAM-1)	After at least 10 hours of fasting * Blood glucose, TG, TC, WBC, platelet count from safety will be also evaluated as clinical risk endpoints
Prior to 11:30 AM		Assessment of cough (VAS)	Irrespective of the time of IP use

Confidentiality Statement

Data and information contained in this document are considered to constitute trade secrets and confidential commercial information, and the legal protections provided to such trade secrets and confidential information are hereby claimed under the provisions of applicable law. No part of this document may be publicly disclosed without the written consent of Philip Morris Products S.A.

Time	Blood Sample	Procedures	Additional Information
Start of Procedure		Day 31 / Day 61	
Before Discharge		Safety urine analysis	
Before Discharge		Information on the risks of smoking, smoking cessation advice and debriefing.	
Before Discharge		Product use diary	To be completed by the subject every day from time of Discharge until next visit. All IPs used including CHTPs 1.2, CC, and any tobacco/nicotine containing products have to be recorded.
Discharge from Visit 2 / Visit 3			

Abbreviations: AE = Adverse event; CC = Combustible cigarette(s); CHTP 1.2 = Carbon Heated Tobacco Product 1.2; IP = Investigational product; SAE = Serious adverse event; VAS = Visual Analogue Scale

Table 17 shows the assessments that will be performed on the first day of Visit 4 of the ambulatory period.

Table 17 Time Schedule – The First Day of Visit 4 (Day 90)

Time	Blood Sample	Procedures	Additional Information
Start of Procedure		Day 90	
Prior to 8:30 AM		Start of Day 90 (the first day of Visit 4)	No product use restriction prior to the opening of the visit Product use will be allowed on site in the CHTP 1.2 and CC arm from the time of check-in in the morning to around 11:00 PM

Confidentiality Statement

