Prior to 11:30 AM	√	Clinical laboratory parameters* (hematology, clinical chemistry) and cardiovascular clinical risk endpoints (hs-CRP, MPO, fibrinogen, homocysteine, , LDL, HDL, HbA1c, sICAM-1, Apo A1, Apo B, 8-epi-PGF2α, PGF2α [‡]), clinical risk endpoints of oxidative stress (4-HNE, TAC)	After at least 10 hours of fasting. * Blood glucose, TG, TC, WBC, platelet count from safety will be also evaluated as clinical risk endpoints [‡] As of 01 June 2016 blood samples for 8-epi-PGF2α/PGF2α will no longer be collected.
Prior to 11:30 AM	√	Bio-banking for BoExp, clinical risk endpoints and other circulating proteins, and transcriptomics, lipidomics and DNA methylation sequencing	If additional consent is signed After at least 10 hours of fasting
Prior to 11:30 AM		Spirometry pre- and post-bronchodilator (recording of FEV ₁ , FVC, FEV ₁ /FVC)	Has to be done prior to use of CC or other nicotine/tobacco-containing products At rest in sitting position for at least 15 minutes prior to pulmonary function testing In sitting position All post-bronchodilator spirometry testing will be performed 15-30 minutes

Confidentiality Statement

Data and information contained in this document are considered to constitute trade secrets and confidential commercial information, and the legal protections provided to such trade secrets and confidential information are hereby claimed under the provisions of applicable law. No part of this document may be publicly disclosed without the written consent of Philip Morris Products S.A.

Time	Blood Sample	Procedures	Additional Information
Start of Procedure		Day 91	
Prior to 11:30 AM	√	CYP2A6 activity in plasma	post administration of salbutamol Has to be done prior to use of CC or other nicotine/tobacco-containing products
Prior to 11:30 AM		Assessment of cough (VAS)	Irrespective of the time of CC or other nicotine/tobacco-containing products use
Before Discharge		ITUQ Questionnaire	
Before Discharge		Vital signs (blood pressure, pulse rate, respiratory rate)	At least 5 minutes in supine position, at least 15 minutes after having stopped using CC or other nicotine/tobacco-containing products
Before Discharge		Physical examination, body weight, and calculated BMI	
Before Discharge		Waist circumference	
Before Discharge		Safety urine analysis	
Before Discharge		Urine pregnancy test (females only)	
Before Discharge		ECG	At least 10 minutes in supine position prior to recording

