U: Bio-banking for BoExp and clinical risk endpoints ⁿ					•					•						•	
B: Bio-banking for transcriptomics, lipidomics and DNA methylation sequencing ^{n, o}				•						•						•	

Abbreviations: 4-HNE = 4-Hydroxy-2-nonenal; 8-epi-PGF2 α = 8-epi-prostaglandine F2 α ; 8-OHdG = 8-Hydroxy-2'-deoxyguanosine; 11-DTX-B2 = 11-dehydro-thromboxane B2; AE = Adverse event; Apo = Apolipoprotein; B = Blood sample required; BMI = Body mass index; BoExp = Biomarker(s) of exposure; CC = Combustible cigarette(s); CHTP 1.2 = Carbon Heated Tobacco Product 1.2; CO = Carbon monoxide; COHb = Carboxyhemoglobin; CYP1A2 = Cytochrome P450 1A2; CYP2A6 = Cytochrome P450 2A6; DNA = Deoxyribonucleic acid; FTND = Fagerström Test for Nicotine Dependence; HbA1c = Hemoglobin A1c; HDL = High density lipoprotein; HIV = Human immunodeficiency virus; hs-CRP = High-sensitive C-reactive protein; LDL = Low density lipoprotein; MCEQ = Modified Cigarette Evaluation Questionnaire; MPO = Myeloperoxidase; PGF2 α = prostaglandine F2 α ; QSU-brief = Questionnaire of Smoking Urges (brief version); SA = Smoking abstinence; SAE = Serious adverse event; sICAM-1 = Soluble inter-cellular adhesion molecule; TAC = Total anti-oxidant capacity; U = Urine sample required; WBC = White blood cell count; TC = Total cholesterol, TG = Triglycerides.

- ^a Systolic and diastolic blood pressure, pulse rate, and respiratory rate (systolic and diastolic blood pressure will also be analyzed as risk markers on Day -1, Day 6, Visit 2, Visit 3, and Visit 4 (first day of the respective visits).
- ^b Including height (only at the Screening Visit).
- ^c Spirometry without bronchodilator will be performed at the Screening Visit (Visit 1) at least 1 hour after having stopped smoking and must be done prior to spirometry with bronchodilator.
Spirometry post-bronchodilator will be done at Visit 1, on Day 6 and at Visit 4. On Day 6 and Visit 4, spirometry post-bronchodilator will be performed prior to product use (CC or CHTP 1.2).
- ^d Pre-study chest X-ray (with anterior-posterior and left lateral views) may be used if performed within 6 months prior to Screening.

Confidentiality Statement

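### Visit 4 blood pressure is a first-day reading in the schedule footnote but is scheduled only on Day 91, after assigned-product use has ended and when CC or other products may already have been used

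*Protocol*

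**What the plan says.** Systolic and diastolic blood pressure at Day 6 and Visits 2, 3 and 4 are secondary cardiovascular risk endpoints (protocol section 3.2, objective 6). Footnote a to the vital-signs row of Table A1 says they will be "analyzed as risk markers on Day -1, Day 6, Visit 2, Visit 3, and Visit 4 (first day of the respective visits"). The SAP's study-assessments appendix carries the same sentence.

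The protocol's section 9.3 time schedules place vital signs on the first day of Visits 2 and 3 (Table 15), timed as "At least 5 minutes in supine position, at least 15 minutes after having stopped using IP". Table 17, for Day 90, has no vital-signs entry. Table 18, for Day 91, lists them before discharge, timed as "At least 5 minutes in supine position, at least 15 minutes after having stopped using CC or other nicotine/tobacco-containing products".

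On product use, protocol section 4.1 states: "The exposure period to the assigned IP will end at 11:00 PM on the first day of Visit 4". CHTP 1.2 packs are handed back at the end of that day (section 6.6.2, Table 17). On Day 91 "subjects who wish to smoke CC or use other nicotine/tobacco-containing products will be allowed to do so", on condition that this follows the end of "24-hour urine collection and after spirometry and sampling for CYP2A6 activity have been performed". Vital signs are not among the conditions. Section 7.3.9 adds that vital signs are measured in the morning.

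SAP section 12.5.2.6 compares the arms at the Day 90 Visit by ANCOVA on the per-protocol populations and does not say which day of the visit supplies the blood-pressure value.

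**The concern.** A named endpoint has a stated time of measurement that the schedule does not deliver. The only scheduled Visit 4 reading comes after the assigned product has been withdrawn. A CHTP 1.2 subject on Day 91 is either abstinent since the night before or using something other than the assigned product. A CC subject is either abstinent or, usually, back on the same kind of product as before. The smoking rule is worded identically for both arms, but it does not put them in the same position.

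What is at stake is the meaning of the Day 90 Visit blood-pressure contrast and of the mean profile over visits. At Visits 2 and 3 the reading is timed against the assigned product, during a period when that product is in use. At Visit 4 it is timed against whatever the subject chose to use that morning.

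**Working it through.** No sample-size, power or alpha figure enters this point. The check sets the passages side by side, works out the Day 91 clock, and tests whether a direction of bias follows.

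**1. Which day?**

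| Source | Visits 2 and 3 | Visit 4 |
|---|---|---|
| Table A1 footnote a; same text in SAP appendix | first day | first day (Day 90) |
| Table A1, vital-signs row | Days 30 and 60 | Day 91; Day 90 blank |
| Section 9.3 time schedules | Days 30 and 60 (Table 15) | none on Day 90 (Table 17); Day 91 (Table 18) |
| SAP 12.5.2.6 | Day 30 and Day 60 Visits | Day 90 Visit, day not named |

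The reading of Table A1 was checked against other rows. The CO breath test, QSU-brief and FTND fall on Day 90, and CYP2A6 and waist circumference on Day 91, all in agreement with Tables 17 and 18. The mismatch is therefore not a displaced column. The vital-signs row of the SAP's own schedule is not legible in the text available, so only its footnote could be compared.

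**2. Can product use precede a morning reading?**

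- Urine collection starts at 09:00 ± 30 min and lasts 24 h ± 1 h. Earliest end: 08:30 + 23 h = 07:30. Latest end: 09:30 + 25 h = 10:30.
- Spirometry and CYP2A6 sampling are due before 11:30 (Table 18).
- Other product use can therefore become allowable from about 07:30, if the other two procedures are done by then, and by about 11:30 if all run to schedule.
- Adding Table 18's 15 minutes, a compliant reading after product use is possible from about 07:45, or from about 11:45 in the latest case. Both are before noon, so the morning rule does not keep the reading ahead of product use.
- From 11 PM to 07:30 is 8.5 hours. Day 91 product use thus comes at least that long after assigned-product use has ended.

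**3. Would the SAP remove such readings?** The ambulatory adherence rule (SAP 11.1, Table 12) applies to the CHTP 1.2 arm and triggers at more than 2 CC in a day, or an average above 0.5 CC per day from Day 1. One or two CC on Day 91 do not meet the first limit. They add at most 2/91 ≈ 0.02 per day to the average. SAP Table 14 gives no window for vital signs.

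**4. Does a direction follow?** Let e_T and e_C be the acute blood-pressure effects of CHTP 1.2 and CC use relative to overnight abstinence. Let p_T and p_C be the shares of each arm that smoke CC before the Day 91 reading. Other products are ignored and longer-term effects are taken as equal on both days.

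- Acute part of the CHTP − CC contrast on the assigned products: e_T − e_C.
- Acute part on Day 91: (p_T − p_C) × e_C.

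The documents give none of these quantities. Assumed values, in units of e_C:

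| e_T | p_T | p_C | On assigned product | Day 91 | Result |
|---|---|---|---|---|---|
| 0 | 50% | 100% | −1 | −0.5 | shrinks |
| 0.5 | 50% | 100% | −0.5 | −0.5 | unchanged |
| 0.5 | 0% | 100% | −0.5 | −1 | widens |
| 0.5 | 75% | 25% | −0.5 | +0.5 | reverses |

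The contrast can move either way.

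**The case against.** The best defence is that this is a drafting slip with little consequence. The first-day parenthesis recurs in footnotes f, g, h, k and l, where it fits the schedule, so it may simply have been carried over into footnote a. Fasting blood markers and waist circumference are also taken on Day 91, so a second-day blood pressure would not be odd. That is plausible. It explains how the conflict could have arisen but leaves the documents in conflict, and it says nothing about product use before the reading.

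The morning rule and the preceding procedures do shorten the interval in which product use could come first. The rule on more than 2 CC would remove some heavier use, and the diary is described as running to discharge at Visit 4 (section 7.7.1), although Table A1 marks it only to Day 90. Both points stand as partial protection. Neither puts blood pressure first, and light use escapes.

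It is also fair that Visits 2 and 3 are not guaranteed to be clean. Table 15 sets no restriction before check-in, and use of other products is tolerated in the ambulatory period. The contrast with Visit 4 is that assigned-product use is still in force at those visits. By Day 91 it has ended by design.

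**Conclusion.** The point holds as an internal contradiction with a measurement gap behind it. No scheduled reading matches the footnote for Visit 4. The reading that is scheduled can follow overnight abstinence, CC use or other product use, and the mix can differ between arms.

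A reader might infer that the comparison is pulled toward no difference, in proportion to the share of the CHTP 1.2 arm that smokes CC on Day 91. The documents do not support that. It requires every CC subject to have smoked and CHTP 1.2 itself to have no acute effect. If CHTP 1.2 subjects stay abstinent while CC subjects have just smoked, the contrast could instead widen. With neither the shares nor the acute effects given, direction and size are undetermined.

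The reach is limited. Blood pressure is one of many secondary endpoints, and SAP 12.1.8 makes no multiplicity adjustment for them. The primary endpoints are untouched: four are taken at Day 5, and the Visit 4 urine collection for total NNAL must end before any Day 91 product use. The change is worth making because it is cheap. Spirometry and CYP2A6 sampling on the same morning already have to precede product use, so the plan recognises the issue for neighbouring measures.

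**What to change.** Reconcile footnote a, Tables A1, 17 and 18 and the SAP footnote on which day's blood pressure is the Visit 4 endpoint, and name that day in SAP 12.5.2.6. If Day 91 is kept, schedule the reading before any CC or other nicotine or tobacco use, next to spirometry and CYP2A6 sampling. The cost is re-ordering one measurement while the subject is already on site.

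Collection may already be over: protocol version 5.0 is dated 05 December 2016 and describes the 4-HNE samples as collected, and the SAP is dated 27 January 2017. In that case only the analysis can change. SAP section 3 allows amendment before database lock. State there that the Day 91 reading is the Day 90 Visit value. Where the time of product use is known, add a sensitivity analysis that excludes readings taken after CC or other product use on Day 91. The diary is described as a daily count, so times may be missing for some subjects; report how many. The cost is one extra secondary analysis on a reduced number of subjects.

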Data and information contained in this document are considered to constitute trade secrets and confidential commercial information, and the legal protections provided to such trade secrets and confidential information are hereby claimed under the provisions of applicable law. No part of this document may be publicly disclosed without the written consent of Philip Morris Products S.A.

- ^e On Day -3 (Admission), after all inclusion/exclusion criteria (see section 5) are checked, eligible subjects will be enrolled and then perform a product test using up to 5 CHTP 1.2. After the product test, subjects not willing and ready to use the CHTP 1.2 will be discontinued.
- ^f CO breath test: During the confinement period on Days -2 to Day 5, the CO breath test will be conducted once per day, preferably in the evening around 08:00 PM \pm 1.5 hour in conjunction (i.e., within 30 minutes) with COHb tests, where applicable. On Day -3 and during the ambulatory period at Visit 2, Visit 3, and Visit 4 (first day of the respective visits), the CO breath tests will be conducted once per day, irrespective of time of product use.
- ^g COHb: Assessments should be done in conjunction (i.e., within 30 minutes) with CO breath tests, where applicable. COHb will be assessed on a daily basis from Day -2 to Day 5. From Day -2 to Day 5, one blood sample for the COHb assessment will be collected in the evening around 08:00 PM \pm 1.5 hour. At Visit 2, Visit 3, and Visit 4 (first day of the respective visits), one blood sample for the COHb assessment will be collected during the visit, irrespective of the time of product use.
- ^h Nicotine/cotinine: From Day -1 to Day 5 (both study arms): one blood sample between 08:00 PM \pm 1.5 hour. On Day 6 (both study arms): one blood sampling between 06:29 AM \pm 1.5 h . At Visit 2, Visit 3, and Visit 4 (first day of the respective visits) in both study arms: one blood sample to be drawn during the visit, irrespective of the time of product use.
- ⁱ As of 01 June 2016, samples for this endpoint will no longer be collected
- ^j Daily during ambulatory period only (from Discharge on Day 6 to Discharge at Visit 4 . Use of any tobacco/nicotine containing products will be captured in the e-diary.
- ^k QSU-brief: Daily, from Day -2 to Day 5 and at every visit during the ambulatory period, i.e., Visit 2, Visit 3 and Visit 4 (first day of the respective visits).

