**Table 14: Assessment Windows**

Assessment	Nominal Time point(s)	Window
	Day 30 Visit, Day 60 Visit and Day 90 Visit	CC arm and prior to use of the first CHTP 1.2 in the CHTP 1.2 arm. Start at 09:00 ± 30 minutes (after bladder void) until 24-hours ±1 hour later.
Spirometry	Screening Day 6 and Day 90 Visit	spirometry without bronchodilator: at least 1 hour after having stopped smoking and prior to spirometry with bronchodilator spirometry with bronchodilator performed 15-30 minutes post administration of salbutamol spirometry will be performed prior to product use (CC or CHTP 1.2). spirometry post-bronchodilator performed 15-30 minutes post administration of salbutamol Day 6: 06:29 AM ± 1.5h Day 91: prior to 11:30 AM
CYP1A2 activity	Day -1, Day 5 and Day 90 Visit	6 hours after intake of cup of coffee ± 15 min
CYP2A6 activity	Day -3, Day 6 and Day 90 Visit	Prior to smoking / product use Day -3 and Day 90 Visit (Day 91): prior to 11:30 AM Day 6: 06:29 AM ± 1.5h
CO breath test	Day -2 to Day 5 Day -3, Day 30 Visit, Day 60 Visit and Day 90 Visit	in the evening around 08:00 PM ± 1.5 hour in conjunction (i.e., within 30 minutes) with COHb tests. First day of the respective visits; irrespective of time of product use
Assessment of Cough	Day -2 to 6 Day 30 Visit, Day 60 Visit and Day 90 Visit	To be done prior to product use but not later than 11:30 AM Second day of the respective visits; prior to 11:30 AM; irrespective of time of product use
Nicotine and cotinine in plasma	Day -1 to Day 6	Day -1 to Day 5: between 08:00 PM ± 1.5 hour. Day 6: between 06:29 AM ± 1.5h.

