12.5.2 Secondary Analyses

12.5.2.1 Biomarkers of Exposure

12.5.2.1.1 Exhaled CO

CO in exhaled breath (expressed as ppm), will be measured using the Micro+™ Smokerlyzer® or similar device, conducted on Day -3 to Day 5, Day 30 Visit, Day 60 Visit and Day 90 Visit.

Descriptive statistics summarized by arm will be produced separately for all timepoints for all visits applicable for exhaled CO. Exhaled CO will be summarized on the natural scale as detailed in Section 12.1.3 “**Descriptive Statistics**”. Distribution will be tested for normality and appropriate non-parametric methods will be used in case of non-normally distributed data as described in 12.1 **General Considerations**.

Actual values and changes from baseline in levels of exhaled CO will be listed and summarized (Table 15.2.4.2.X and Listing 15.3.3.1). In addition line graphs will be produced for arithmetic means (and 95% CI) per randomization arm over all timepoints (Figure 15.1.2.5).

An ANCOVA model on exhaled CO (Day 5 and Day 90 Visit) will be used with terms for the baseline value, sex, average cigarette consumption over the previous 6 weeks prior to Admission and arm. The LS means on Day 5 and Day 90 for each arm along with the difference (CHTP 1.2 - CC) and 95% confidence interval (CI) will be presented in the tables (Table 15.2.4.1).

The statistical model and SAS code for the analysis of exhaled CO on Day 5 and at Day 90 Visit and COHb at Day 90 Visit will be the same as described in Section 12.5.1.1 “**Primary endpoints**”; except that there will be no log transformation of the data and back-transformation of the LS Means estimates of the difference.

If applicable, the table with descriptive statistics will be repeated for the group of subjects who attempt to quit (see section “**10.7 Quitters Population**”)

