12.5.2.2 Nicotine and Cotinine Concentrations

It is assumed that Nicotine and Cotinine concentrations are log-normally distributed.

The descriptive analysis will be the same as described in Section 12.5.1.1 “Primary endpoints”.

The percent change from baseline will be calculated. The concentrations of nicotine and cotinine will be listed and summarized along with this change (Table 15.2.4.15 and Listing 15.3.4.1). Line graphs of the nicotine and cotinine concentration profiles across all study days showing geometric mean and 95% CI will also be produced (Figure 15.1.2.28).

Nicotine and cotinine values will also be analyzed in a repeated measures mixed model on the log-transformed values, as described in section “12.5.2.1.3 NEQ” (Table 15.2.4.16).

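### COHb, exhaled CO and plasma nicotine/cotinine are timed to the evening through Day 5 but not at Visits 2-4, so profiles and changes from baseline mix time of day with product effect

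*Protocol*

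**What the plan says.** Table A1 in Protocol Appendix A sets the times in its footnotes.

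- COHb in confinement: "From Day -2 to Day 5, one blood sample for the COHb assessment will be collected in the evening around 08:00 PM", with a tolerance of 1.5 h. At Visits 2-4: "one blood sample for the COHb assessment will be collected during the visit, irrespective of the time of product use".
- Exhaled CO on Day -2 to Day 5: "the CO breath test will be conducted once per day, preferably in the evening around 08:00 PM". At Visits 2-4: "the CO breath tests will be conducted once per day, irrespective of time of product use".
- Plasma nicotine/cotinine: evening window from Day -1 to Day 5, no clock time at Visits 2-4. Day 6 has its own dawn window, which SAP Table 14 repeats: "Day 6: between 06:29 AM", again ± 1.5 h.

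Protocol Tables 15 and 17 also give no clock time for these samples on the first day of the visits. Protocol section 9 lets a procedure without a stated start time be done whenever suits during the day.

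SAP Table 17 takes as baseline the last valid value before exposure, which for these measures is the Day -1 evening sample. SAP 12.5.2.1.1 compares exhaled CO (Day 5, Day 90 Visit) and COHb (Day 90 Visit) with the primary ANCOVA, "except that there will be no log transformation of the data". Its terms are baseline, sex, cigarette consumption and arm. For nicotine and cotinine, SAP 12.5.2.2 states: "Nicotine and cotinine values will also be analyzed in a repeated measures mixed model on the log-transformed values". Sampling times are listed (Listings 15.3.3.1 and 15.3.4.1) but enter no model.

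**The concern.** Nicotine clears within hours (half-life 1-2 h in Protocol Appendix D), and CO is assumed here to do so too. Their level depends on how much of the day's product use precedes the draw. A morning value at Visit 2, 3 or 4 set against an evening baseline can show a fall with no change in exposure.

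This touches pre-specified output: the secondary objectives on CO, COHb and nicotine over the whole exposure period, the line graphs over all timepoints, the changes from baseline, and the Visit 4 ANCOVAs. On the natural scale, a proportional fall shared by both arms cancels in a ratio but not in a difference, so the reported Visit 4 difference depends partly on the site's working hours.

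The nicotine model raises a related point. Nine post-baseline samples appear to enter it: five evening (Days 1-5), one dawn (Day 6) and three untimed (Visits 2-4). The SAP does not list them. Day 6 is inferred from its definition of the exposure period, which runs to discharge on Day 6, and from the title of Table 15.2.4.16.

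**Working it through.** **1. The plan's own figure.** Protocol Table 23 gives 96% test-wise power for COHb on Day 5. Inputs: mean ratio 0.40, CV 0.32, 50% threshold, 80 versus 40, one-sided 2.5%.

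- Log-SD = √ln(1 + 0.32²) = 0.312; distance to threshold = ln(0.50/0.40) = 0.223.
- z = 0.223 / (0.312 × √(1/80 + 1/40)) = 3.69; power = Φ(3.69 − 1.96) = 95.8%.

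The figure is reproduced and does not change, because baseline and Day 5 are both evening samples.

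**2. An early draw at Visits 2-4 (worst case).** Assume steady use from 06:30 after a 7.5 h overnight gap, and a CO half-life h of 2-6 h. The level t hours after 06:30, relative to plateau, is L(t) = 1 − (1 − 0.5^(7.5/h)) × 0.5^(t/h). An 08:30 draw has t = 2; 8 PM has t = 13.5.

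| h (hours) | L(2) | L(13.5) | ratio |
|---|---|---|---|
| 2 | 0.537 | 0.991 | 0.54 |
| 3 | 0.481 | 0.964 | 0.50 |
| 4 | 0.486 | 0.930 | 0.52 |
| 5 | 0.510 | 0.900 | 0.57 |
| 6 | 0.540 | 0.878 | 0.61 |

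So an 08:30 draw reads roughly 0.50-0.62 of the 8 PM level.

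**3. Draws spread over the day.** Assume draws evenly spread over 08:30-23:00, h of 3-5 h, and a repeating daily pattern with use from 06:30 to 23:00.

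- Geometric mean: 0.86-0.87 of the 8 PM level, an apparent fall of 13-14%.
- Added log-SD: 0.17-0.18, against at most 0.014 inside the evening window.
- The natural-scale difference follows the arithmetic mean. With k = ln 2/h and a the level at 06:30, this is 1 − (1 − a)(e^(−2k) − e^(−16.5k))/(14.5k), divided by the 8 PM level. For h = 4: a = 0.261, giving 0.809/0.929 = 0.87. If both arms share the daily pattern and draw times, the difference shrinks by about the same 13%.

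**4. What the noise costs.** No power is stated for Visit 4 COHb, and its test is not against a 50% threshold, so this is only an illustration. Use CV 0.32 and 40 versus 40, since the plan assumes at least 50% of the CHTP 1.2 arm stays in the ambulatory per-protocol set.

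- No timing noise, 50% threshold: z = 0.223/(0.312 × √(2/40)) = 3.20; power 89%.
- Log-SD √(0.312² + 0.17²) = 0.356 to √(0.312² + 0.18²) = 0.360: power about 79-80%.
- Against a ratio of 1, as in the SAP hypothesis: above 99.9% either way.

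**5. Day 6 nicotine.** Use stops at 11 PM, 7.5 h before 06:30.

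- Half-life 1 h: 0.5^7.5 = 0.6% left; 2 h: 0.5^3.75 = 7.4%.
- If the overall LS mean weights nine timepoints equally on the log scale, this one sample multiplies it by 0.0055^(1/9) = 0.56 to 0.074^(1/9) = 0.75 in each arm.
- Cotinine (half-life 16-18 h in Appendix D) keeps 0.5^(9/16) = 68% to 0.5^(6/18) = 79% across the Day 6 window.

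**The case against.** The strongest reply is that nothing confirmatory is touched. Day 5 COHb is evening against evening. The other four primary endpoints and nicotine equivalents come from 24-hour urine. The nicotine objective is descriptive, secondary endpoints carry no multiplicity-controlled claim, and protocol and SAP agree on the timing. All of this stands and limits the weight of the point.

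A reader might infer that the Visit 4 contrasts are biased between arms. The documents do not support that: one rule covers both arms, and nothing indicates that draw times differ by arm. Open-label conduct makes it possible, no more. A shared proportional fall shrinks the difference and cannot create one.

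A reader might also take an early-morning figure as the general effect. A draw 1 h into the day reads 35-57% of one at 12 h (half-life 2-6 h), but only if everyone is sampled then after the overnight gap. That gap is a confinement rule; before Visits 2-4, product use is unrestricted until the visit opens.

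Nor does Day 6 distort the nicotine arm ratio. The model is on the log scale, and a proportional drop common to both arms goes into the timepoint term. (This reads timepoint as a factor, as the SAP text suggests; the printed code puts a different variable name in the CLASS statement.) What remains is that overall LS means average evening, dawn and untimed values.

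A real-world aim for the ambulatory phase does not require untimed sampling: product use stays unrestricted by amount whatever the sampling hour.

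**Conclusion.** The point holds as a cheap improvement to secondary results. From Visit 2 on, profiles, changes from baseline and Day 5 versus Visit 4 comparisons cannot separate time of day from product effect. For the Visit 4 arm differences the cost is mainly noise and some shrinkage.

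The CO sizes rest on assumed half-lives and steady use from 06:30: a 13-14% fall for evenly spread draws, and 0.50-0.62 of the evening level for an 08:30 draw as the worst case. Actual draw times are not in the documents, so the real shift may be smaller. The Day 6 nicotine figure rests on the protocol's own half-life. It makes that sample a trough, but it does not invalidate the arm comparison, and it does not carry over to cotinine with the same force.

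**What to change.** For any visits still to come, take COHb, exhaled CO and nicotine/cotinine on the first day of Visits 2-4 at 8 PM ± 1.5 h, as in confinement. Subjects are already on site, may use their product until 11 PM and complete questionnaires between 8 and 11 PM. The cost is an evening blood draw at three visits plus protocol and SAP wording; no sample or visit is added.

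For samples already drawn, amend the SAP before database lock:

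- Add recorded sampling time as a covariate in a sensitivity analysis of the Visit 4 COHb and exhaled CO models.
- Mark the change of sampling time on the line graphs and change-from-baseline tables.
- Keep Day 6 nicotine out of the pooled repeated-measures estimate and summarise it separately as a trough. For cotinine this is optional; state the choice.

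This second part costs only SAP text and programming.
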